### 9.3.5 Abuse

Abuse relates to the sporadic or persistent, intentional excessive use of an IMP which is accompanied by harmful physical or psychological effects.

The term abuse must be documented on the AE form of the eCRF. In addition, AEs originating from abuse must be documented on a separate line.

### 9.3.6 Aggravation of Condition

Any clinically significant aggravation/exacerbation/worsening of any medical condition(s), compared to baseline, must be reported as an AE.

## 9.4 Additional Reporting Requirements for Serious Adverse Events

### 9.4.1 Investigator Reporting Responsibilities

Any SAE must be reported to LEO Pharma K.K on the LEO Serious Adverse Event Form (paper) - Clinical Trials within 24 hours of first knowledge.

This report should contain an assessment of available information on seriousness, severity, causal relationship to the IMP, comparator or trial procedure, the action taken, the outcome to date, and a narrative description of the course of the event.

The completed SAE form must be faxed or scanned and e-mailed to LEO Pharma K.K. using the following fax number or e-mail address:

[contact]

E-mail address: [contact]

It may be relevant for the (sub)investigator to enclose other information with the SAE form, such as anonymised reports of diagnostic procedures, hospital records, autopsy reports, etc.

Additionally, Global Safety, LEO Pharma A/S may request further information in order to fully assess the SAE. The (sub)investigator must forward such information to Global Safety, LEO Pharma A/S via LEO Pharma K.K. upon request by fax or e-mail (see contact details above).

The investigator must report SAEs to the director of the trial site. The director of the trial site must notify the local IRB(s) of SAEs as required by current applicable legislation for the concerned country.

SAEs occurring after the completion of the clinical trial, including the protocol required post-treatment follow-up period, should not be routinely sought or collected. However, such events should be reported to LEO Pharma K.K. if the (sub)investigator becomes aware of them.

#### **9.4.2 LEO Pharma Reporting Responsibilities**

Global Safety, LEO Pharma A/S is responsible for assessing whether or not a SAE is expected. The relevant reference document for those randomised to LEO 90100 foam is the current version of the Investigator's Brochure for LEO 90100 foam. For those randomised to Dovobet® ointment, the relevant reference document is the Japanese package insert for Dovobet® ointment.

Global Safety, LEO Pharma A/S and LEO Pharma K.K. (collectively called as 'LEO Pharma') will notify the regulatory authorities and concerned investigators of SAEs according to the current applicable legislation for the concerned country.

The IRB(s) will be notified of SAEs according to the current applicable legislation for the concerned country. For Japanese sites, the investigator and LEO Pharma K.K. will be notified of the IRB review outcome by the director of the trial site.

All SAEs which are assessed as causally related to the IMP(s) by either the investigator or LEO Pharma A/S, and which are not expected (Suspected, Unexpected Serious Adverse Reactions (SUSARs)) are subject to expedited reporting to regulatory authorities and IRB(s) according to the current applicable legislation in the concerned country. Investigators will be notified of these on an ongoing basis. In addition, in Japan all SAEs which are assessed as causally related to the IMP(s) by either the investigator or LEO Pharma A/S and are subject to expedited reporting in Japan, will be reported to regulatory authorities, IRB(s) and investigators according to the current applicable legislation in Japan.

## 9.5 Follow-up for Final Outcome of Adverse Events

During the trial, the investigator should follow up for final outcome on all AEs (including SAEs). Once a subject leaves the clinical trial, the investigator should follow up on the outcome of all non-serious AEs classified as of possible/probable relationship to the IMP for 14 days or until the final outcome is determined, whichever comes first. All related and not related SAEs must be followed up until a final outcome has been established, i.e. the follow-up may continue beyond the end of the clinical trial.

## 9.6 Handling of an Urgent Safety Measure

An Urgent Safety Measure is a measure taken to implement an action/protocol deviation under an emergency. This is defined within the EU Directive as “...*the occurrence of any new event relating to the conduct of the trial or the development of the investigational medicinal product where that new event is likely to affect the safety of the subjects, the sponsor and the investigator shall take appropriate urgent safety measures to protect the subjects against any immediate hazard.*” (Article 10(b) of Directive 2001/20/EC).

If the investigator becomes aware of information that necessitates an immediate change in the clinical trial procedure or a temporary halt to the clinical trial in order to protect clinical trial subjects from any immediate hazard to their health and safety, the investigator can do so without prior approval from LEO Pharma, regulatory authority(ies) or IRB(s).

The investigator must immediately inform LEO Pharma K.K. of this change in the clinical trial procedure or of the temporary halt providing full details of the information and the decision making process leading to the implementation of the urgent safety measure.

LEO Pharma K.K. must act immediately upon receipt of the urgent safety measure notification in accordance with the internal procedures and local legislation.

## 10 Investigational Medicinal Products

### 10.1 Investigational Medicinal Product Description

Finished product (brand) name (if available)/name of IMP	LEO 90100 foam
Formulation	Foam
Active ingredient name/concentration	Calcipotriol hydrate 52.2 µg/g (equivalent to 50.0 µg/g calcipotriol) plus betamethasone dipropionate 0.643 mg/g
Excipients	Paraffin, white soft Paraffin, liquid Polyoxypropylene stearyl ether All-rac-alpha-tocopherol Propellants: Dimethyl ether Butane
Pack size	60 g can
Sites involved in manufacturing, labelling or release	
 
• LEO Laboratories Ltd, [name]
 
• LEO Pharma A/S, [name]
 
• Colep Laupheim GmbH & Co. KG, [name]
 
• Klifo A/S, [name]
 

Finished product (brand) name (if available)/name of IMP	Dovobet® ointment
Formulation	Ointment
Active ingredient name/concentration	Calcipotriol hydrate 52.2 µg/g (equivalent to 50.0 µg/g calcipotriol) plus betamethasone dipropionate 0.643 mg/g
Excipients	Paraffin, white soft Paraffin, liquid Polyoxypropylene stearyl ether All-rac-alpha-tocopherol
Pack size	30g tube
Sites involved in manufacturing, labelling or release	
 
• LEO Laboratories Ltd, [name]
 
• LEO Pharma A/S, [name]
 
• Klifo A/S, [name]
 

## 10.2 Administration of Investigational Medicinal Products

Route of administration	Topical
Dosing range	Depending on the size of psoriasis lesion
Dosing frequency	Once daily
Weekly maximum	60g

The instructions for use, as detailed on the subject treatment instructions, are as follows:

*For subjects receiving tubes:*

- Remove the cap and break the seal of the tube using the point in the back of the cap. Turn the cap round while still pushing to create a round hole.
- Squeeze the ointment onto a clean finger
- Apply with the fingertips

*For subjects receiving cans:*

- Keep the cans in the supplied outer carton, to protect from light.
- The can should be shaken for a few seconds before use.
- Application can be performed by either applying after spraying directly on the affected areas or by spraying in the palm and applying on to the affected areas with the fingertips.
- Use enough to cover each lesion. Apply gently with fingertips
- Apply the study medication by holding the spray can at least 3cm from the skin and spray.

*For both groups of subjects:*

- Apply the trial medication to psoriasis once daily.
- Apply trial medication first to the ‘target lesion’, as instructed by the trial doctor, and then apply to other lesions to the extent possible for lesions that may be hard to reach, namely on the back.
- Take care not to spread the medication onto unaffected skin
- Avoid accidental contact to the face, eyes or mouth
- Wash hands after each application
- Do not use the trial medication on any psoriasis on the face, scalp, genitals or skin folds (armpits, groin, under the breasts, those around the buttocks and the perianal area)
- Do not use any other treatments on psoriasis, apart from medication which the (sub)investigator may prescribe for use on psoriasis on the face, scalp, genitals or skin folds
- If taking a bath/shower or washing hair around the time of medication application, apply the medication afterwards (to avoid washing it off). However, do not apply trial

P-001 - Clinical Trial Protocol (template); version 23-Jan-2015

medication or emollients on the target lesion before coming to the site on the day of the Visits.

- Do not bandage or otherwise cover or wrap the treated areas
- Avoid excessive exposure of treated areas to either natural or artificial sunlight (including tanning booths, sun lamps, etc.)
- Keep the medication out of the sight and reach of children and pets
- The medication is for external use only
- Return all medication at each visit
- After applying, avoid contact with textiles which are easily stained by grease, e.g. silk

The subject treatment instructions will be explained to the subject at Visit 1, and the subject will be given a copy. A subject trial card will also be given out at Screening visit.

Subjects with the target lesion achieving ‘substantial resolution’, as defined in section 5, before the end of 4 weeks’ treatment will complete the trial at this time (although will still be required to attend the follow-up visit up to 14 days later, if applicable).

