Subjects will be provided with 60g of medication per week. Approximately 20.2g of ointment covers the whole body (29). Hence, approximately 6.1g of ointment covers 30% BSA, the maximum area to which medication can be applied in this trial. This is equal to 42.7g per week as the maximum once daily dosage of ointment. Since LEO 90100 foam has the same composition as Dovobet® ointment, with the exception of the propellants, it should be able to cover at least the same area as the ointment. Therefore, 60g per week should be an adequate amount of medication to provide to the subjects.

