6.7.1 Exposure

In addition to what is stated in the CTP (section 11.3.3), the number of days of exposure will be calculated as the date of final application minus the date of first application plus 1,

ignoring any interim missing applications. The duration of exposure to treatment (weeks) will be derived as the number of days of exposure divided by 7, and will be summarized for each treatment group using the mean, SD, median, minimum and maximum values. The sum of duration of exposures to treatment will be presented as all subjects-treatment-weeks.

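### Protocol 10.2 gives a coverage instruction to the foam arm only; any wording on amount should be the same in both arms

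*Protocol*

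**What the plan says.** Protocol 10.2 has a short administration table covering both products, then three lists of subject instructions: one for tubes, one for cans and one for both groups. The instructions are explained at Visit 1 and the subject is given a copy.

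- **Cans (foam):** besides storage, shaking and spraying directions, the list says "Use enough to cover each lesion. Apply gently with fingertips".
- **Tubes (ointment):** the list covers opening the tube, then "Squeeze the ointment onto a clean finger", then applying with the fingertips. It has no wording on amount or coverage.
- **Both groups:** once daily, target lesion first and then other lesions, sites to avoid, and keeping the product off unaffected skin. It has no wording on amount or coverage.
- **Common table:** the dosing range is "Depending on the size of psoriasis lesion", once daily, with one weekly maximum for both products.

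On measurement, Protocol 11.3.3 defines compliance as missed applications divided by days. SAP 6.7.1 states that "the number of days of exposure will be calculated as the date of final application minus the date of first application plus 1", converted to weeks and summed to subject-treatment-weeks. SAP Table 201 has the word extent in its title, but the SAP text defines only duration. Protocol 10.7.1 requires a subject-level inventory of product given and returned, and the SAP plans Listing 2.5.2 for drug accountability.

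**The concern.** The primary objective is to compare the efficacy of two formulations with the same active ingredients at the same concentrations (Protocol 4.1 and 10.1). How thoroughly the target lesion is covered is one route by which the arms could differ for a reason unrelated to formulation. An instruction to cover each lesion is not device handling, because it could be given equally well for an ointment. Giving it to one arm only adds a difference between the arms that the design does not need.

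The trial is open, and part of the primary endpoint is an investigator's judgement of general change, so blinding offers no protection. If the wording affected how fully subjects treated the lesion, some of the observed difference could belong to the instruction sheet. The planned summary tables would not help a reader to judge this, because none of them describes amount used.

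**Working it through.** **1. Do the written instructions differ?**

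| Source in Protocol 10.2 | Applies to | Wording on amount or coverage |
|---|---|---|
| Administration table | both arms | scaled to lesion size, with a weekly maximum |
| List for cans | foam | cover each lesion (qualitative, no grams) |
| List for tubes | ointment | none |
| List for both groups | both arms | none |

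The table is common to both arms, but it stands outside the listed subject instructions. Within those lists, only foam subjects are told to cover each lesion.

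**2. What would the planned outputs show?** Compliance (Protocol 11.3.3) counts missed applications. Exposure (SAP 6.7.1, Table 201) counts days and weeks. A subject who applied a thin or partial layer every day would have full compliance and full exposure. Listing 2.5.2 gives accountability by subject. With one 60 g can or two 30 g tubes making up each week's 60 g, it could reveal gross differences in product used. It is a listing, with no summary or comparison by arm.

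**3. The plan's only figures on amount.** Protocol 3.3 justifies the supply as follows: "Approximately 20.2g of ointment covers the whole body (29") and "approximately 6.1g of ointment covers 30% BSA". These reproduce: 20.2 × 0.30 = 6.06, rounded to 6.1 g per application, and 6.1 × 7 = 42.7 g per week, against 60 g supplied. They describe total use over the largest treatable area. The primary endpoint is scored on one target lesion, so they neither support nor weaken this point.

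**4. Illustration of size.** The documents give no effect of the wording on amount or response, so every shift here is assumed. Inputs: 90 per arm (Protocol 6.2), two-sided 5% (Protocol 11.3.10), Fisher's exact test (Protocol 11.3.4), an assumed foam response of 80%, and an assumed ointment response of 80% less 0, 3, 5 or 8 points.

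- Standard error of the difference = √[p₁(1 − p₁)/90 + p₂(1 − p₂)/90]. For 80% against 80% this is √(0.16/90 + 0.16/90) = 0.060. For 80% against 72% it is √(0.16/90 + 0.2016/90) = 0.063.
- Probability of a significant result in favour of foam = the sum of Bin(a; 90, 0.80) × Bin(b; 90, p₂) over all tables with a > b and two-sided Fisher p ≤ 0.05, where a and b are the foam and ointment responders.

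| Assumed ointment response | Shift | Significant in favour of foam |
|---|---|---|
| 80% | 0 | 1.6% |
| 77% | 3 points | 5.0% |
| 75% | 5 points | 9.1% |
| 72% | 8 points | 19.1% |

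Swapping the arms gives the same percentages in favour of ointment, so direction is an input to this calculation and not a result of it.

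**The case against.** The strongest reply is that the common text already covers the matter. Both arms have a dosing range tied to lesion size, the same weekly maximum and the same once-daily instruction. Telling someone to apply ointment to a lesion arguably implies treating all of it. The foam line sits among spraying directions, and a spray lacks the visible quantity that a squeezed tube gives. Much of this stands: the foam wording is qualitative, and it would be wrong to say that only one arm is told a dose. It does not explain why a coverage sentence that suits either product appears in one list only.

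A reader might infer that unequal dosing is built into the comparison. The documents do not support that. They show a difference in wording, not a difference in use, and nothing indicates a direction. The randomised comparison of the two products as instructed remains valid. What is less secure is attributing a difference to formulation alone.

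A reader might also infer that unequal use could never be detected. That is too strong as well. Containers are returned at Visits 2 to 4, a subject-level inventory is kept, Listing 2.5.2 is planned, and Protocol 10.7.3 records missed applications or other deviations with the help of a diary.

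A third tempting argument is that the supply exceeds the stated need by 60 − 42.7 = 17.3 g per week, so supply does not equalise use. That is true of total use, but it says nothing about the amount on the single lesion that is scored.

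**Conclusion.** The point holds as a minor one. The written instructions differ between the arms on coverage, the difference is avoidable, and it carries a risk that part of any difference in target-lesion response comes from the instruction. The risk is not demonstrated, and the documents give neither its size nor its direction.

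The percentages of 5%, 9% and 19% against 1.6% rest wholly on an assumed 80% response and assumed losses of 3, 5 and 8 points in the ointment arm. They show what a bias of that size would do at 90 per arm. They are not evidence that this sentence causes one. Because the planned tables do not summarise amount, an imbalance in use would be seen at most coarsely, through the accountability listing.

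**What to change.** Reconcile the lists in Protocol 10.2 and in the subject treatment instructions so that any wording on amount is identical in both arms. It can stand once in the list common to both groups, or be left out of both product-specific lists. The choice and the wording are for the sponsor. The product-specific lists should keep only device handling.

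The cost is one line moved or removed in the protocol and the instruction sheet, made through the usual amendment and approval route in Appendix 5A where that applies. There is no effect on sample size, visits or analysis.

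Weighing returned containers is not part of this recommendation. It would be an extra procedure, the grams would mix all treated lesions with the scored one, and the weight lost from foam cans would include propellant whose share the documents do not give.

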### **10.3 Precautions/Over dosage**

#### Calcipotriol

Calcipotriol may cause hypercalcaemia. Serum calcium is quickly normalised, however, when treatment is discontinued. In addition, calcipotriol may cause decline in kidney function associated with hypercalcaemia. The major symptoms of hypercalcaemia include malaise, feelings of weakness, anorexia, nausea, vomiting, enlarged feeling of abdomen, abdominal pain, headache, dizziness, muscle pain and muscle weakness.

#### Betamethasone dipropionate

AEs found in connection with systemic corticosteroid treatment, such as adrenocortical suppression or impact on the metabolic control of diabetes mellitus, may occur also during topical corticosteroid treatment due to systemic absorption.

There may be a risk of generalised pustular psoriasis or of rebound effects when discontinuing treatment. Medical supervision should therefore continue in the post-treatment period.

### **10.4 Packaging of Investigational Medicinal Products**

The IMPs will be packaged in individually numbered kits. Primary and secondary packaging materials will be individually labelled. The details of the primary and secondary packaging are described in the trial product manual.

The labelling of IMPs must be in accordance with EU GMP Annex 13, local regulations and trial requirements.

## 10.5 Storage of Investigational Medicinal Products

All LEO Pharma supplied IMPs must be stored in a secure and restricted area under the conditions specified on the label. At the investigational site, they should not be stored above 30°C, and not stored in a freezer. IMPs must remain in the original container until dispensed. The cans of LEO 90100 foam must be dispensed to the subject in the carton each can is supplied in, in order to protect it from light.

## 10.6 Treatment Assignment and Dispensing

At Visit 1, subjects who have been found to comply with all the inclusion and exclusion criteria will be randomised to receive treatment with either LEO 90100 foam or Dovobet® ointment. Treatment assignment will be pre-planned according to a computer-generated randomisation schedule in a 1:1 ratio, stratified by investigator site. Randomisation will be performed by a sealed envelope method at site. After confirming subject's eligibility criteria, (sub)investigator opens only the corresponding envelope that contains treatment assignment in the predefined order, i.e. by specifying which of the two treatments the subject should receive. The person who opened the envelope writes the date, time and name on the envelope. The site can then choose any available outer box with the assigned medication for the subject. Full details of this randomisation procedure will be given in a separate document.

From this outer box, IMP is dispensed to the subject at Visits 1, 2 and 3. At Visit 1, the carton labelled 'Week 1' is dispensed. At Visit 2, the carton labelled 'Week 2' is dispensed. At Visit 3, the cartons labelled 'Week 3' and 'Week 4' are dispensed, and the subject should be instructed to use the medication labelled 'Week 3' for the next week, and then the medication labelled 'Week 4' for the subsequent week.

At Visits 2, 3 and 4, the medication dispensed at Visits 1, 2 and 3, respectively, should be returned by the subject, including any empty cans/tubes, and retained by the site for collection.

### 10.6.1 Randomisation Code List

The randomisation schedule will be prepared by LEO Pharma A/S or CRO. It must not be provided to investigator site staff.

## **10.7 Drug Accountability and Compliance Checks**

### **10.7.1 Drug Accountability**

The director of the trial site is fully responsible for the IMPs at the trial site and the IMP administrator is responsible for maintaining adequate control of the IMPs and for documenting all transactions with them in Trial Medication Inventory Log.

At Visit 2, 3 and 4, the IMP (including empty containers) dispensed at Visits 1, 2 and 3, respectively, must be returned by the subject. An inventory at subject level must be kept of the IMP given to and returned by each subject in the trial. This inventory must be available for inspection during monitoring visits and will be checked by the monitor to ensure correct dispensing of the IMP.

All IMPs supplied by the Contract Manufacturing Organisation (CMO) on behalf of LEO Pharma must be returned to the CMO. Prior to their return, they must be fully accounted for by the monitor with the help of the person responsible for dispensing the IMPs. Accountability must be documented by using drug accountability forms. IMPs will be returned from the trial site to the CMO. The IMP returned to the CMO will be reconciled with the Trial Medication Inventory Log.

